[figure not shown]
[figure not shown]

## Study information

[figure not shown]
Title	Treatment patterns with targeted therapies in metastatic renal cell carcinoma (mRCC) in Sweden – A retrospective analysis of data from national registries.
Protocol number	A6181234
Protocol version identifier	Version 2.0
Date	13 April 2021
Active substance	L01XE04 (sunitinib) L01XE17 (axitinib)
Medicinal product	Sutent, Inlyta
Research question and objectives	The objectives of this study are to investigate treatment patterns and outcomes for sunitinib and axitinib mRCC patients in a nationwide population-based setting in Sweden.
Author	PPD [REDACTED] PhD PPD [REDACTED] Sweden PPD [REDACTED]

## 2. LIST OF ABBREVIATIONS

Abbreviation	Definition
AE	Adverse event
AEM	Adverse event monitoring
ATC	Anatomical Therapeutic Chemical
CDR	Cause of Death Register
CI	Confidence interval
CRF	Case report forms
DCT	Data collection tool
GPP	Guidelines for Good Pharmacoepidemiology Practices
ICD	International Classification of Diseases
IEC	Independent ethics committee
IRB	Institutional review board
ISPE	International Society for Pharmacoepidemiology
ISPOR	International Society for Pharmacoeconomics and Outcomes Research
KM	Kaplan Meier
mRCC	metastatic renal cell carcinoma
mTOR	mammalian target of rapamycin
NBHW	National Board of Health and Welfare
NI	Non interventional

PFIZER CONFIDENTIAL

[figure not shown]
NIS	Non interventional study
NPR	National Patient Register
OS	Overall Survival
PDR	Patient Drug Register
PIN	personal identification number
RCC	Renal cell carcinoma
SCR	Swedish Cancer Register
SPC	Summary of Product Characteristics
TKI	tyrasine kinase inhibitor
TNF	tumor necrosis factor
VEGF	vascular endothelial growth factor
YRR	your reporting responsibilities

#### 4. AMENDMENTS AND UPDATES

Amendment number	Date	Protocol section(s) changed	Summary of amendment(s)	Reason
1	April 13, 2021	8.2	Change from 30 days grace period to 90 days in base case, when calculating treatment duration	Too many of the patients with a switch from 4:2 to 2:1 are lost with a 30 day grace period. The rational to move to 90 days is that the likelihood of having a longer gap is higher than that the patients get a treatment in the gap (it also has to be a treatment that we cannot see, we capture all oral treatments, which makes it even more unlikely)
2	April 13, 2021	8.1, 8.2	Time period for data collection modified; end date for data collection is changed to 31 December 2019	Access to data from SoS

PFIZER CONFIDENTIAL

## 5. MILESTONES

Milestone	Planned date
Milestone	Planned date
Start of data collection	15 December 2020
End of data collection	31 March 2021
Final study report	31 March 2021

[figure not shown]
## 6. RATIONALE AND BACKGROUND

Renal cell carcinoma (RCC) accounts for approximately 2% of all cancers worldwide, with the highest rates observed in North America, Australia and Europe [1]. In Western, Northern and Southern Europe, a total of over 87,000 patients are diagnosed with RCC each year, leading to an estimated 33,000 deaths [2]. RCC is often asymptomatic, or associated with non-specific symptoms such as fatigue, weight loss, fever and anemia [3]. Many patients present with advanced or unresectable disease, and around 30% of patients treated by nephrectomy for localized disease will relapse [4].

The worldwide and European annual increase in RCC incidence is approximately 2%, however in Denmark and Sweden, a continuing decrease has been observed during the last two decades [5]. In 2016, there were 1267 new cases of renal malignancy (excluding the renal pelvis) reported in Sweden, of which a majority was above 65 years of age [6]. The Swedish RCC death ratio reaches approximately 550 cases per year.

With the advent of modern targeted therapies, the prognosis of patients with metastatic RCC (mRCC) has improved. From a median survival of about a year, the new therapies reached a survival of over 2 years [7, 8]. These agents include the multitargeted receptor tyrosine kinase inhibitors (TKI) sunitinib (Sutent®, Pfizer Inc.), sorafenib (Nexavar®, Bayer HealthCare/Onyx Pharmaceuticals), pazopanib (Votrient®, GlaxoSmithKline Inc),

PFIZER CONFIDENTIAL

axitinib (Inlyta®, Pfizer Inc), cabozantinib (Cabometyx®, Ipsen), tivozanib (Fotivda®, EUSA Pharma), lenvatinib (Kisplyx®, EISAI), the vascular endothelial growth factor (VEGF) ligand-binding monoclonal antibody bevacizumab (Avastin®, Genentech, Inc.) and the mammalian target of rapamycin (mTOR) kinase inhibitors temsirolimus (Torisel®, Pfizer Inc) and everolimus (Afinitor®, Novartis).

Great progress in the area of immunotherapy with nivolumab (Opdivo®, BMS) and the combinations nivolumab/ipilimumab (Opdivo®/Yervoy®, both BMS), pembrolizumab/axitinib, (Ketruda®/Inlyta®, MSD and Pfizer) and avelumab/axitinib (Bavencio®/Inlyta®, Merck and Pfizer) has also been made in recent years that will benefit patients with metastatic RCC. In such revolutionized treatment landscape, where immunotherapy-based combinations are the new standard of care, TKI monotherapy maintains a role in the treatment of certain mRCC patients who are not suitable for immunotherapy [9]. Notably, TKI monotherapy is still today in Sweden the recommended treatment for the subgroup of patients with favourable prognosis [10].

To date, limited information on real-world treatment patterns such as dosing and time from initiation to discontinuation or drug survival exist in the mRCC setting. For other disease areas drug survival is commonly analyzed in Europe and in the United States, see Hetland et al (2010) for an analysis of tumor necrosis factor (TNF) inhibitors [11].

Wahlgren et al (2013) and Lindskog et al (2017), to some extent investigate mRCC treatment patterns in the Swedish setting but in a more general manner [12, 13]. Both these studies demonstrate a statistically significant improved survival for the Swedish mRCC patients treated with targeted therapies compared to no or a hormonal/chemotherapeutic intervention. In Redig et al (2019) the improved survival from modern targeted therapy is put in relation to the increased cost [14].

During the last years studies investigating effects on safety and outcomes from different dosing schedules have been published, focusing on sunitinib and mostly based on smaller  
PFIZER CONFIDENTIAL

[figure not shown]
selected patient populations. Bracarda et al (2017) carried out a critical review of published studies until then and found that although the studies had a low level of evidence, the results indicated that the 2:1 schedule improved tolerability compared with the 4:2 schedule. Regarding efficacy no definitive conclusions could be drawn due to the methodologic limitations of the available studies [15].

Another example of study in this area is Bracarda et al (2015) where a retrospective sample of 249 mRCC patients is analysed. The authors found a longer drug survival for patients that moved to a modified 2:1 schedule, both compared to patients that started on a 2:1 schedule and patients that did not modify the dosing scheme. They also found that patients who moved to a 2:1 schedule experienced an improved safety profile compared to during the initial 4:2 schedule [16]. Crumbaker et al (2018) investigated 63 Australian mRCC patients and found that patients starting on a 2:1 dosing schedule had a drug survival that was longer than the overall survival (OS) times seen in the trials using the 4:2 schedule [17]. Boegemann et al (2018) evaluated efficacy and safety regarding sunitinib treatment modification in first line treatment of mRCC and found that in addition to mitigating adverse events (AEs), sunitinib treatment modification may help improve efficacy outcomes by prolonging treatment duration [18].

There is a need for additional research in this area and so far no studies based on Swedish data has been carried out. The current study aims at analyzing sunitinib drug survival and overall survival for Swedish mRCC patients treated in first line, and investigate how these outcomes are affected by different dosing schedules. The study will also investigate axitinib drug survival and overall survival in second line. Safety will not be analysed in this study due to the characteristics of the available data.

Sweden has a unique opportunity in its large number of health data registers run by the National board of Health and Welfare (NBHW). These long-history, high-quality, registers constitute the foundation of a very successful Swedish research tradition in the field of clinical epidemiology, and cover health data in the entire population that is easily

PFIZER CONFIDENTIAL

accessible by researchers. From July 2005, the Prescribed Drug Register (PDR), covers date and amount of medication prescribed and dispensed to the patient. It also stores personal identification number, which enables linkage to other registers. The National Patient Register (NPR) covers inpatient care episodes and outpatient visits, including information of procedures (i.e. surgery) and diagnosis codes. The Swedish Cancer Register (SCR) (since 1958) contains tumor and pathology data from all patients diagnosed with cancer in Sweden. The national Cause of Death Register (CDR) (1961) contain information on the cause of death.

Combining data from these four registers creates an opportunity to derive patterns of duration of treatment and overall survival for the full Swedish mRCC cohort.

## **7. RESEARCH QUESTION AND OBJECTIVES**

The present study is an explorative retrospective study investigating treatment patterns and outcomes for sunitinib and axitinib mRCC patients in a nationwide population-based setting in sweden.

In more detail the primary objective is to:

- Investigate time to treatment discontinuation (treatment duration) for first line treatment with sunitinib for different treatment schedules: 4:2 (4 weeks on/2 weeks off) and 2:1 (2 weeks on/1 week off).

The secondary objectives are to:

- Investigate overall survival (OS) for first line treatment with sunitinib, for different treatment schedules, 4:2 (4 weeks on/2 weeks off) and 2:1 (2 weeks on/1 week off).
- For second line treatment with axitinib, investigate time to treatment discontinuation (treatment duration) and OS.

## 8. RESEARCH METHODS

### 8.1. Study design

To address the research objectives, the study will be carried out as a national retrospective population-based register study based on data from the NBHW.

Based on the study objectives, the primary endpoint in this study is:

- Time to treatment discontinuation in first line sunitinib patients. Time to event measure from index date to discontinuation of treatment, from 01 July 2005 to 31 December 2019 (assessed from index date up to 180 months). This will be investigated using Kaplan-Meier analysis.

[figure not shown]
### 8.2. Setting

The data used for the analyses includes all patients aged  $\geq 18$  years with at least one filled prescription of an oral targeted therapy relevant for treating mRCC registered in the Swedish Prescribed Drug Register between 01 July 2005 (there is no data available in the register before this date) and 31 December 2019. The Anatomical Therapeutic Chemical (ATC) codes for the oral drugs relevant for treating mRCC are the following: L01XE04 (sunitinib), L01XE05 (sorafenib), L01XE11 (pazopanib), L01XE17 (axitinib), L01XE10 (everolimus), L01XE26 (cabozantinib), L01XE34 (tivozanib), L01XE29 (lenvatinib).

Selecting patients based on dispensed prescriptions ensure that all patients that have prescriptions on the relevant drugs are included in the analyses. The first identified prescription date will correspond to the patient's index date that is relevant for capturing the age.

The PDR does not provide any information on mRCC, which is the area of interest in this study. The analysis therefore combines the PDR, the SCR and the NPR with the aim to identify the mRCC cohort. The patients identified in the PDR that also are identified in the SCR with the International Classification of Diseases and Related Health Problems

PFIZER CONFIDENTIAL

(ICD)-7 diagnosis codes I800 or I809 and ICD-10 codes C64.0 and C64.9 from 01 January 2000 until 31 December 2019; excluding ICD-7 code I801 (cancer of the renal pelvis) will be included in the analysis set.

The mRCC cohort derived above will then be further restricted into two different analysis sets that will be used to carry out the analyses.

[figure not shown]
- Analysis Set 1: patients treated with sunitinib in the first line mRCC setting
- Analysis Set 2: patients treated with axitinib in the second line mRCC setting

Analysis Set 1 will be derived in the following way, from the full mRCC cohort described above, individuals will be selected that have sunitinib as the first filled prescription (the earliest date) of the relevant drugs: (sunitinib), L01XE05 (sorafenib), L01XE11 (pazopanib), L01XE17 (axitinib), L01XE10 (everolimus), L01XE26 (cabozantinib), L01XE34 (tivozanib), L01XE29 (lenvatinib), and L03AB (cytokines medication). L03AB used to be a common treatment for this patient group in the beginning of the investigated period and is therefore needed to identify the correct treatment line.

Analysis Set 2 will be derived in the following way, from the full mRCC cohort described above, individuals will be selected that have axitinib as the second filled prescription (the earliest date) of the relevant drugs: (sunitinib), L01XE05 (sorafenib), L01XE11 (pazopanib), L01XE17 (axitinib), L01XE10 (everolimus), L01XE26 (cabozantinib), L01XE34 (tivozanib), L01XE29 (lenvatinib). In addition, to secure that axitinib is used as a second line treatment (i.e. not third line), L03AB (cytokines medication) is not allowed to have been dispensed before axitinib.

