**Table 3. Variables extracted from the NBHW**

Variable	Explanation	Data source(s)
ICD7	ICD-7 code	Swedish Cancer Register
ICD9	ICD-9 code	Swedish Cancer Register
ICDO10	ICD-O/2-10	Swedish Cancer Register
ICDO3	ICD-O/3	Swedish Cancer Register
ALDER	Age at diagnosis	Swedish Cancer Register
M	Spread of tumor at diagnosis, distant metastases	Swedish Cancer Register
N	Spread of tumor at diagnosis, Lymph nodes	Swedish Cancer Register
DIADAT	Date of RCC diagnosis	Swedish Cancer Register
DODSDAT	Date of death	Swedish Cancer Register
DODSDATN	Date of death numeric	Swedish Cancer Register
KON	Gender	Swedish Cancer Register
SJUKHUS	Hospital where diagnosis was set	Swedish Cancer Register
DODSDAT	Date of death	Swedish Cause of Death Register
ALDER	Age at visit	National Patient Register
AR	Year of visit	National Patient Register
MVO	Medical focus area	National Patient Register
SJUKHUS	Hospital	National Patient Register
DIAGNOS	Diagnosis	National Patient Register
HDIA	Main diagnosis	National Patient Register
KON	Sex	National Patient Register

PFIZER CONFIDENTIAL

INDATUMA	Date for start of visit	National Patient Register
OP	Surgery	National Patient Register
UTDATUMA	Date for end of visit	National Patient Register
VTID	Duration of care	National Patient Register
ALDER	Age at the end of the year	Swedish Prescribed Drug Register
ARBLAN	The region of the prescribing clinic	Swedish Prescribed Drug Register
FDATE	Prescription date	Swedish Prescribed Drug Register
EDATE	Dispense date	Swedish Prescribed Drug Register
ANTAL	Number of packages	Swedish Prescribed Drug Register
DOSER	Dosing instructions	Swedish Prescribed Drug Register
EXPLAN	Region/County of dispensing pharmacy	Swedish Prescribed Drug Register
FVARUNR	Dispensed drug goods number	Swedish Prescribed Drug Register
ATC	ATC code	Swedish Prescribed Drug Register
PRODUKT	Name of product	Swedish Prescribed Drug Register
FORPS	Package size	Swedish Prescribed Drug Register
STYRKALF	Strength of the product	Swedish Prescribed Drug Register
STYRKAENHET	Unit of the strength	Swedish Prescribed Drug Register
KON	Gender	Swedish Prescribed Drug Register

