## **8.9. Limitations of the research methods**

The retrospective design entails a risk of bias in the analyses, especially selection and misclassification bias. Furthermore, information on medication not dispensed on prescription (medication administered in a hospital) is not available at the NBHW. This will have as a consequence that potentially not all patients treated with oral targeted mRCC drugs are included in the analysis. Selecting patients based on dispensed prescriptions and a registered RCC diagnosis might have the consequence that some included patients also suffer from other malignancies for which they were treated with one of the specified drugs. However, we

PFIZER CONFIDENTIAL

believe that risk to be small. Insights from previous studies using this type of data (Wahlgren et al (2013) and Lindskog et al (2017)) will help us handle this in the best way possible. One additional limitation that concerns the definition of treatment line is that the data only allows us to evaluate the chronological order of received treatments, but no data on disease progression is available.

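### The cohort rule does not require the RCC diagnosis to precede the first fill, so OS can include guaranteed survival time and treatment for another tumour can be counted as first-line mRCC

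*Combined protocol and SAP*

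**What the plan says.** Section 8.2 starts from adults with a fill of a listed oral drug "registered in the Swedish Prescribed Drug Register between 01 July 2005" and the end of 2019. It keeps "The patients identified in the PDR that also are identified in the SCR" with a qualifying kidney cancer code. The diagnosis window reads "from 01 January 2000 until 31 December 2019; excluding ICD-7 code I801 (cancer of the renal pelvis) will be included in the analysis set". Section 8.4 repeats the same rule.

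The time origin follows the fill: "The first identified prescription date will correspond to the patient's index date". Section 8.2.1 starts OS, and the treatment episode, at the first dispensed package.

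Both analysis sets are then derived from the order of fills alone. For Set 1, "individuals will be selected that have sunitinib as the first filled prescription (the earliest date) of the relevant drugs"; for Set 2, "individuals will be selected that have axitinib as the second filled prescription (the earliest date) of the relevant drugs". Set 2 also bars an earlier cytokine fill. Neither set carries a condition on the diagnosis date.

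Table 3 in 8.6 lists DIADAT, described as "Date of RCC diagnosis", among the extracted variables. No step in 8.2, 8.4, 8.6 or 8.7 uses it for selection or for time zero.

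Section 8.9 concedes that "some included patients also suffer from other malignancies for which they were treated with one of the specified drugs". It regards the risk as small and says that experience from two earlier Swedish studies will help in dealing with it.

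**The concern.** The two windows overlap and are independent of each other. A first sunitinib fill in 2007 and an RCC record in 2017 satisfy the rule as well as the reverse order does. The 2007 fill would then be the index date of a first-line mRCC patient.

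Two different problems follow.

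- **OS (secondary objective).** Such a patient is in the data only because they were alive at the later diagnosis. The time from fill to diagnosis is immortal time created by selecting on a future event, and it is counted as OS follow-up.
- **Time to treatment discontinuation (primary endpoint).** The episode starting at the early fill may have treated another tumour. It is nevertheless analysed as first-line sunitinib for mRCC.

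Set 2 is affected in its own way. OS there starts at axitinib, so guaranteed time arises only if axitinib itself preceded the diagnosis. An earlier fill of another listed drug for another tumour would instead be counted as the first line, so that axitinib is labelled second line when it may not be.

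The Cox covariates in 8.7 (age, gender, year of initiation, region) cannot correct any of this.

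**Working it through.** **Reading the rule**

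| Step | Date condition in the plan | Diagnosis before fill required? |
|---|---|---|
| PDR selection (8.2, 8.4) | fill 1 July 2005 to 31 December 2019 | no |
| SCR selection (8.2, 8.4) | diagnosis 1 January 2000 to 31 December 2019 | no |
| Set 1 (8.2) | sunitinib is the earliest relevant fill | no |
| Set 2 (8.2) | axitinib is the second relevant fill, no earlier cytokine | no |
| OS and treatment start (8.2.1) | first dispensed package | no |

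The longest possible gap from fill to diagnosis is the fill window: 14 × 12 + 6 = 174 months, or 14.5 years. That is a single extreme, not a typical value.

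**Size for OS**

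The only figure in the plan is about 1,000 first-line sunitinib patients (8.5). It comes without inputs, so it cannot be reproduced. The rest is assumption:

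- f, the share with a fill before diagnosis: 0.5%, 1% and 3% (5, 10 and 30 of 1,000).
- S0(t) = 2^(−t/M), exponential OS for correctly ordered patients, with M = 24 months. Section 6 says only that survival exceeds 2 years.
- g, the gap from fill to diagnosis. A mis-ordered patient has survival 1 up to g and S0(t − g) afterwards.

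The observed curve is S(t) = (1 − f)·S0(t) + f·S1(t), where S1 is the mis-ordered curve. When g is at least as long as the quantile in question, S1 = 1 there. The time at which S = p is then

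t_p = M · log2[(1 − f)/(p − f)].

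This is the largest value the model gives for any g.

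| f | Median, p = 0.5 (true 24.0) | Q3, p = 0.25 (true 48.0) |
|---|---|---|
| 0.5% | 24 · log2(0.995/0.495) = 24.2 | 24 · log2(0.995/0.245) = 48.5 |
| 1% | 24 · log2(0.99/0.49) = 24.4 | 24 · log2(0.99/0.24) = 49.1 |
| 3% | 24 · log2(0.97/0.47) = 25.1 | 24 · log2(0.97/0.22) = 51.4 |

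Point estimates at f = 3%:

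- 36 months, g = 36: 0.97 × 35.4% + 3% = 37.3%, against 35.4%.
- 60 months, g = 60: 0.97 × 17.7% + 3% = 20.1%, against 17.7% (computed from unrounded values).

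Shorter gaps do less. At f = 1% and g = 12 the median is 24.1. The shifts scale with M: at M = 30 and f = 3% the maxima are 31.4 against 30 and 64.2 against 60.

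**Small schedule group**

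If mis-ordered patients made up 10% of one schedule group (an assumption well above the range used for the whole set), the median could reach 24 · log2(0.90/0.40) = 28.1 months.

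**Time to treatment discontinuation**

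No comparable calculation applies. Under 8.2.1 the episode ends when supply runs out (90-day grace period), at a fill of another relevant drug, or at death. Survival to a later diagnosis rules out only the last of these before that diagnosis.

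**The case against.** **The number affected may be very small.** To enter through treatment for another tumour, a patient must take a listed drug for that tumour, survive, and then receive an RCC diagnosis by the end of 2019. Nothing in the documents shows that even one patient did, and the 0.5-3% range is assumed. This stands.

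**Within that range the shift lies inside sampling error for the whole set.** With 1,000 patients, no censoring and λ = ln 2/24 = 0.0289 per month, the 95% half-width is 1.96·√[p(1 − p)/1000]/(pλ). That is about 2.1 months for the median and 3.7 months for Q3, against maximum shifts of 1.1 and 3.4. This also stands. But the half-width describes random error, whereas this shift works in one direction and can be avoided.

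**The primary endpoint is not stretched.** A reader might infer that guaranteed survival inflates the tail of treatment duration as it does OS. The documents do not support that, because an episode that ended years before the diagnosis is not lengthened by surviving to it. What remains is a possibly wrong indication, of unknown direction.

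**A later diagnosis date does not prove another tumour.** It may reflect late dating of genuine RCC, so a strict order rule can remove true mRCC patients. The rule also leaves in patients diagnosed with RCC first who later took the drug for a different cancer. Both points stand and shape the fix.

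**Section 8.9 already acknowledges the issue.** It does, and it states an intention to handle it. But it gives no rule, check or count, and does not mention date order or guaranteed survival time.

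**Conclusion.** The point holds. Followed as written, 8.2 and 8.4 admit patients whose OS includes time in which they could not have died, and whose treatment episode may belong to another disease. This is more than missing detail, because applying the stated rule produces a wrong inclusion.

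For OS the guaranteed time acts upward. With 0.5-3% affected and exponential OS with a 24-month median, the median moves by about 1 month at most and Q3 by up to about 3 months. At 1% or less, both shifts are about a month or smaller. The effect could be larger in the far tail, where Table 4 reports the maximum and late point estimates, or in a small schedule group. These figures also assume that survival after the late diagnosis matches that of other patients.

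A reader might go further and conclude that the published OS will be materially wrong, or that the primary endpoint carries immortal time. The documents support neither: they give no count of mis-ordered patients, and the discontinuation endpoint is affected only through misclassified indication and, in Set 2, treatment line. The change is worth making because it is cheap and turns an unquantified belief into a reported number.

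**What to change.** **Main analysis.** In 8.2 and 8.4, require DIADAT on or before the first fill of any listed drug, and report the number excluded from each analysis set and, in Set 1, from each schedule group.

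**Sensitivity analyses.**

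1. Allow a short window after the first fill, with its length fixed in advance, so that genuine mRCC patients with a late-dated diagnosis are retained.
2. Exclude patients with another cancer recorded in the NPR fields DIAGNOS or HDIA before the first fill. This is too broad for the main analysis, since it also drops mRCC patients with an unrelated earlier cancer.

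**Limitations.** In 8.9, replace the statement that the risk is believed small with the observed counts.

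**Cost.** One filter on a variable already extracted and two repeat runs. A few genuine mRCC patients with a late-dated diagnosis may be lost from the main analysis; the first sensitivity analysis shows whether that matters. If the count is near zero, the sponsor loses almost nothing and its own assessment of the risk is confirmed.
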